2.4.5.2 Deaths

The following summaries of deaths will be generated for the safety population.

Statistical Analysis Plan
LPS15023 - Dupilumab

15-Mar-2021
Version number: 2.0

- Number (%) of patients who died by study period (TEAE, on-study) and reasons for death.
- TEAE leading to death (death as an outcome on the AE eCRF screen as reported by the Investigator) by primary SOC, HLGT, and PT showing number (%) of patients.

2.4.5.3 Analyses of laboratory variables

Continuous data will be summarized by visit using the number of available data (n), mean, standard deviation (SD), median, minimum, and maximum and change from baseline where appropriate. Categorical and ordinal data will be summarized by visit using the number and percentage of patients.

Clinically significant test results will be recorded as AEs; overall AE summaries will include the AEs reported in the study (see Protocol 11.4.3.1) and the clinical significant test results that are recorded as AEs.

2.4.5.4 Analyses of physical examination and vital sign variables

Symptom-driven physical examination and vital signs will be performed in patients presenting with signs or symptoms. Continuous data will be summarized by visit using the number of available data (n), mean, standard deviation (SD), median, minimum, and maximum and change from baseline where appropriate. Categorical and ordinal data will be summarized by visit using the number and percentage of patients.

2.4.5.5 Analyses of electrocardiogram variables

Not applicable

2.4.5.6 Analyses of COVID-19-related variables

The number and percentage of patients with impact due to COVID-19 will be summarized using the number of patients with at least 1 impacted site visit, the number of patients with at least 1 visit with different impact type (visit not done, visit partially done, visit delayed), the number of visit types (vital signs, local laboratory hematology, pregnancy tests, physical examination and follow-up, investigational product administration, and contact form), and the number of patients impacted per visit. Wave 3 analyses will be performed by assessment and visit type, and stratified by country (France, Canada, and Israel). COVID-19-related analysis will also include Argentina and South Africa in the final analysis.

2.5 DATA HANDLING CONVENTIONS

General conventions

Not applicable

Statistical Analysis Plan
LPS15023 - Dupilumab

15-Mar-2021
Version number: 2.0

2.5.1 Data handling conventions for secondary efficacy variables

Not applicable

2.5.2 Missing data

For categorical variables, patients with missing data are not included in calculations of percentages unless otherwise specified. When relevant, the number of patients with missing data is presented.

Handling of computation of treatment duration if investigational medicinal product end of treatment date is missing

For the calculation of the treatment duration, the date of the last dose of IMP is equal to the date of last administration reported on the end-of-treatment case report form page. If this date is missing, last available dose date + 11 days will be used.

The last dose intake should be clearly identified in the case report form and should not be approximated by the last returned package date.

Handling of medication missing/partial dates

No imputation of medication start/end dates or times will be performed. If a medication date or time is missing or partially missing and it cannot be determined whether it was taken prior or concomitantly, it will be considered a prior, concomitant, and posttreatment medication.

Handling of adverse events with missing or partial date/time of onset

Missing or partial adverse event onset dates and times will be imputed so that if the partial adverse event onset date/time information does not indicate that the adverse event started prior to treatment or after the treatment-emergent adverse event period, the adverse event will be classified as treatment-emergent. No imputation of adverse event end dates/times will be performed. These data imputations are for categorization purpose only and will not be used in listings. No imputation is planned for date/time of adverse event resolution.

Handling of adverse events when date and time of first investigational medicinal product administration is missing

When the date and time of the first IMP administration is missing, all adverse events that occurred on or after the day of randomization should be considered as treatment-emergent adverse events. The exposure duration should be kept as missing.

The last dose intake should be clearly identified in the case report form and should not be approximated by the last returned package date.

Statistical Analysis Plan
LPS15023 - Dupilumab

15-Mar-2021
Version number: 2.0

Handling of missing assessment of relationship of adverse events to investigational medicinal product

If the assessment of the relationship to IMP is missing, then the relationship to IMP is assumed to be possibly related in summary tables, but no imputation will be presented in the listings.

Handling of missing severity of adverse events

If the severity is missing for 1 of the treatment-emergent occurrences of an adverse event, the maximal severity on the remaining occurrences will be considered. If the severity is missing for all the occurrences, a “missing” category will be added in the summary table.

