8.1.3 Dose schedule

The IMP will be administered every 14±3 days (q2w). The consecutive doses of the IMP must be separated by ≥11 days to avoid an overdose. If in TRAVERSE the patient was already self-injecting, and/or parent/caregiver(s) was already injecting the patient, the Investigator or delegate will supervise the injection, or the Investigator or delegate will train the patient (and/or parent/caregiver[s]) on how to prepare and inject IMP at Start-of-treatment Visit (Visit 1) and will inject the first injection. For patients who discontinued treatment for ≥6 weeks after TRAVERSE ie, patients requiring a loading dose, the first injection is the first of the 2 injections of IMP (for the 600 mg dose).

Reminder: patients will be monitored for any signs or symptoms of hypersensitivity reactions for a minimum of 30 minutes after IMP injection on-site visit days. For patients who experience hypersensitivity reactions upon retreatment, ie, at the Start-of-treatment Visit (Visit 1), or for patients with long off-treatment interval after the completion of TRAVERSE, additional on-site IMP administration visits may be scheduled at the Investigator's discretion.

Subcutaneous injection sites should be alternated between the 4 quadrants of the abdomen (avoiding navel and waist areas), the upper thighs, or upper arms (lateral side), so that the same site is not injected twice consecutively. Injection in the upper arms could be done only by a trained person (parent/caregiver[s] trained by the Investigator or delegate) or health care professional but not the patient themselves. This instruction pertains to the day of the loading dose as well as for subsequent q2w injections. For each injection, the anatomic site of administration will be recorded in the electronic case report form (eCRF) and in the home-dosing diary.

Detailed instructions for transport, storage, and administration of IMP will be provided to the patient, and Investigators should ensure that these instructions are followed. Patients will complete a home-dosing diary to document compliance with self-injection (or parent/caregiver injection) of IMP.

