1 OVERVIEW AND INVESTIGATIONAL PLAN

1.1 STUDY DESIGN AND RANDOMIZATION

The LPS15023 study is a Phase IIIb, non-randomized, open-label, interventional, outpatient, prospective, multinational, multicenter, noncomparative, single-arm, safety study in patients with moderate to severe asthma who completed the parent study, TRAVERSE-LTS12551, from here on referred to as TRAVERSE.

This study will evaluate the long-term safety of dupilumab 300 mg q2w administered subcutaneously (SC) over a maximum of 144 weeks.

It is expected that approximately 750 patients will enroll in this study.

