2.4.5.1 Analyses of adverse events

Analysis of Primary Safety Endpoint

Incidence rates of TEAEs with corresponding 95% CI (by the Clopper-Pearson method) will be calculated as follows:

- Incidence Rate (IR) = number patients with one or more TEAEs / number of subjects at risk (i.e. safety population) × 100

Event rates per 100 person-years of TEAEs with corresponding 95% CI (two-sided exact Poisson CIs) will be calculated. All events reported during the study follow-up period will be counted, regardless of whether they are reported in the same subject (i.e., multiple events per subjects), or different subjects. The person-years at follow-up will be calculated using the standard on-treatment duration formula: (the date of last IMP – date of first dose of IMP + 14 days)/365.25. Note that date of first dose of IMP, is in regards to first dose of this study, not first dose of the parent study. Event rate per person-years will be calculated as follows:

- Event rate (ER) = number of TEAEs / number of person-years at follow up

Analysis of Secondary Safety Endpoints

Incidence rates with corresponding 95% CI (Clopper-Pearson method) and event rates with corresponding 95% CI (exact Poisson method) will be presented for AESIs, described in [section 2.1.4.1](#), using the same methodology described above.

Incidence rates with corresponding 95% CI (Clopper-Pearson method) will be presented for SAEs/death over the study.

Incidence rates with corresponding 95% CI (Clopper-Pearson method) will be presented for AEs leading to study discontinuation over the study.

Generalities

The primary focus of adverse event reporting will be on treatment-emergent adverse events.

Statistical Analysis Plan
LPS15023 - Dupilumab

15-Mar-2021
Version number: 2.0

If an adverse event date/time of onset (occurrence, worsening, or becoming serious) is incomplete, an imputation algorithm will be used to classify the adverse event as pretreatment, treatment-emergent, or posttreatment. The algorithm for imputing date/time of onset will be conservative and will classify an adverse event as treatment emergent unless there is definitive information to determine it is pretreatment or posttreatment. Details on classification of adverse events with missing or partial onset dates are provided in [Section 2.5.3](#).

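### SAP 2.5.2 handles a missing first-dose date with an anchor this non-randomized study lacks and leaves exposure missing, so an affected patient adds events but no person-time to the primary event rate

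*SAP*

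**What the plan says.** **Event rate.** SAP 2.4.5.1 defines "Event rate (ER) = number of TEAEs / number of person-years at follow up". Person-years per patient come from "the date of last IMP – date of first dose of IMP + 14 days)/365.25". The same section counts every event reported during follow-up, including repeats in one patient.

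**Missing first-dose date.** SAP 2.5.2 says that adverse events occurring "on or after the day of randomization should be considered as treatment-emergent adverse events". It then says: "The exposure duration should be kept as missing".

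**Design.** SAP 1.1 calls the study "non-randomized, open-label, interventional", and SAP 2.2.1, on randomization irregularities, is marked not applicable. Protocol 8.4 supplies a dated event that does exist: a patient is enrolled, at Visit 1, when the IRT assigns a treatment kit number.

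**Missing last-dose date.** The source is the form completed when treatment ends, and SAP 2.5.2 states its scope first: "For the calculation of the treatment duration, the date of the last dose of IMP is equal to the date of last administration reported". Where that form lacks the date, the rule is: "If this date is missing, last available dose date + 11 days will be used". No reason is given for the 11 days. They match the minimum spacing in Protocol 8.1.3: "The consecutive doses of the IMP must be separated by ≥11 days to avoid an overdose".

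**The concern.** The event rate is half of the primary endpoint, and it is interpretable only if the same patients supply its events and its person-time. The first-dose rule breaks that link. It tells the programmer to start counting events from a date that no patient has, and to leave the same patient's exposure blank. A patient who was dosed but has no first-dose date still belongs to the safety population (SAP 2.3.2), so the events stay in the count while the person-years vanish. The error runs one way, upward.

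The last-dose rule raises a lesser question. It places the last dose 11 days after the last recorded one, and the exposure formula then adds its usual 14 days. In effect it credits one further, undocumented injection. The SAP does not say whether this imputed date is meant only for exposure or also for the end of the treatment-emergent window.

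**Working it through.** The plan states no power, precision or event-count figure. The 750 is an expected enrolment, so there is nothing of the plan's own to reproduce.

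**Inputs from the documents**
- Expected patients: 750 (SAP 1.3).
- Maximum treatment: 144 weeks = 1008 days (SAP 1.1).
- Exposure: last dose − first dose + 14 days (SAP 2.4.3.1 and 2.4.5.1).
- Dosing every 14 ± 3 days, so at least 14 − 3 = 11 days apart (Protocol 8.1.3).
- Treatment-emergent window: last dose + 14 days for completers, + 84 days for premature discontinuation (SAP 2.4.5).

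**Assumptions, not in the documents**
- Mean exposure 364 to 1008 days.
- 1 to 10 patients with no first-dose date.
- 1% to 25% of patients with no last-dose date.
- 200 TEAEs per 100 person-years, used only to gauge precision.

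**1. First-dose rule**

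Let E be all events, PY all true person-years and p the person-years of the affected patients. The intended rate is E/PY. As written it is E/(PY − p). The relative error is therefore p/(PY − p), and the number of events cancels.

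If m affected patients have average exposure, this becomes m/(750 − m):
- 1 patient: 1/749 = 0.13%
- 5 patients: 5/745 = 0.67%
- 10 patients: 10/740 = 1.35%

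The figure depends on how long the affected patient was treated. With mean exposure of 364 days, total exposure is 750 × 364 = 273,000 days. One patient with the full 1008 days gives 1008/(273,000 − 1008) = 0.37%. One patient with a single dose gives 14/(273,000 − 14) = 0.005%.

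For scale, total person-years are 750 × 364/365.25 = 747.4 to 750 × 1008/365.25 = 2069.8. At the assumed event rate the exact Poisson 95% interval has a half-width of about 5.1% and 3.1% of the rate respectively.

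**2. Last-dose rule**

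Credit after the last recorded dose is 11 + 14 = 25 days, against 14 with nothing added. The error depends on what happened after that record:
- No further dose: +11 days.
- One further dose at 11, 14 or 17 days: 0, −3 or −6 days.
- Six further doses at 14-day intervals (a 12-week gap in the records): 11 − 84 = −73 days.

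In the first case, exposure is overstated by 11/1008 = 1.1% at full duration, 11/364 = 3.0% at one year, and 11/14 = 79% for a patient with a single recorded dose. Pooled over the study, with a share f affected, person-time rises by f × 11/mean exposure. At f = 25% and 364 days this is 0.76%, which lowers the rate by 0.75%. At f = 1% and 1008 days it is 0.01%.

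If the imputed date also set the treatment-emergent window, the window would end 11 + 14 = 25 days (completers) or 11 + 84 = 95 days (premature discontinuation) after the last recorded dose.

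**The case against.** **On the first-dose rule.** The first injection is given or supervised on site at Visit 1, with 30 minutes of monitoring, at the visit where the kit is allocated. A missing date should therefore be very uncommon. The randomization wording looks like carried-over template text, and most programmers would read it as enrolment. Adverse events are recorded from consent, so that reading would change few classifications. The SAP also has no sentence specific to missing-exposure patients that keeps their events in the numerator. The rarity and the likely reading both stand, and they limit the size of the problem. They do not repair the text. SAP 2.4.5.1 counts all events without exception, and reading randomization as enrolment still leaves exposure missing.

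**On the last-dose rule.** A reader might infer that the added 11 days inflate person-time for patients who disappear early, and that they lengthen the treatment-emergent window too. The documents support neither as a general statement. Patients inject at home between 12-weekly visits, carry enough kits to reach the next visit, and hand back their dosing records only at visits. A patient who stops attending may have taken several undated doses, in which case 11 days is too few. Adding nothing assumes that no such dose was taken, which is no better verified. SAP 2.5.2 words the rule for treatment duration only, so an effect on the window is an open question and not a stated consequence.

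**Conclusion.** The first-dose rule is wrong as written: its anchor does not exist in this study, and it separates events from person-time. The bias is upward, about 0.13% of the event rate per affected patient out of 750, assuming that patient has average exposure. The number of such patients is unknown and probably near zero. Even ten would move the rate by 1.35%, which is inside the interval half-width of about 3% to 5% under the assumed event rate and exposure. This is a correction of definition, with little consequence for the result.

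The last-dose rule is an unexplained choice and not a demonstrated error. It can overstate, match or understate exposure, and its pooled effect on the rate stays below 1% with up to 25% of last-dose dates missing, if mean exposure is at least 364 days. It would be a mistake to conclude that numerator and denominator are wrong for every patient with a missing dose date.

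**What to change.** In SAP 2.5.2:

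1. Replace the randomization date with the Visit 1/IRT kit allocation date.
2. Replace the instruction to leave exposure missing. For any dosed patient without a first-dose date, impute that date as the Visit 1/IRT kit allocation date, so that the patient enters both numerator and denominator.
3. For a missing last-dose date, give the reason for the 11 days and state whether the imputed date also sets the end of the treatment-emergent window. At most, add a sensitivity analysis using the last documented dose date with nothing added.

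The cost is a few sentences of SAP text. No new data are needed, since the kit allocation date is already in the IRT database. The optional sensitivity analysis is one rerun of the event-rate table.

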2.5.3 Windows for time points

Not applicable – no analysis by visit/window.

2.5.4 Unscheduled visits

Not applicable – no analysis by visit/window.

2.5.5 Pooling of centers for statistical analyses

Not applicable

2.5.6 Statistical technical issues

Not applicable

Statistical Analysis Plan
LPS15023 - Dupilumab

15-Mar-2021
Version number: 2.0

3 INTERIM ANALYSIS

Interim analyses of data may be conducted to support regulatory submissions or publication activities.

Statistical Analysis Plan
LPS15023 - Dupilumab

15-Mar-2021
Version number: 2.0

4 DATABASE LOCK

The database is planned to be locked at 4 weeks after last patient last visit.

Additional database snapshots/soft locks may be performed to support regulatory submissions.

Statistical Analysis Plan
LPS15023 - Dupilumab

15-Mar-2021
Version number: 2.0

5 SOFTWARE DOCUMENTATION

All summaries and statistical analyses will be generated using SAS Enterprise Guide 7.1 and SAS studio 3.7.

Statistical Analysis Plan
LPS15023 - Dupilumab

15-Mar-2021
Version number: 2.0

6 REFERENCES

Not applicable

Statistical Analysis Plan
LPS15023 - Dupilumab

15-Mar-2021
Version number: 2.0

7 LIST OF APPENDICES

Not applicable
